9.8.1 End of Subject Participation in Study/Completion of Study

After the study has been completed (or in case of early termination), subjects will be exited from the study. Subjects will continue to work with their physician after study exit per normal standard of care. The clinical investigation is considered completed once the last subject has exited the study.

9.8.2 Lost to Follow-Up

If a subject does not return to the investigational center for required follow-up visit(s) and cannot be reached, the investigational center staff should make 3 documented attempts to contact the subject by phone to verify if the subject should be considered "lost-to follow up". In the event the subject is not able to perform follow-up visits at the investigational center, subject will be considered "lost to follow up" and this needs to be documented in the Study Exit eCRF. All efforts will be made by investigation center staff to collect all study devices and supplies back from subject, if applicable.

9.9 Study Stopping Rules

The study may be stopped if the Data Monitoring Committee (DMC) determines that there are significant safety issues, including the occurrence of certain types of individual adverse events (i.e. UADE, device related DKA, device related HHS and device related Severe Hypoglycemia) that have undergone expedited adjudication by the Clinical Events Committee (CEC). See CEC **Section 12.1** and DMC **Section 12.2** for more details regarding the expedited review responsibilities of both committees.

10. Risks and Benefits

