11.6 Causality Assessment

An AE is not automatically related to the study device or procedure simply because the subject is wearing the device and participating in the study. The event should be reviewed to determine if the device or study procedure could have possibly caused the event and therefore is related to the study device or procedure.

Causality assessment is the determination of the relationship between an AE and the device being studied. It is expected that the investigational center will review all elements surrounding the AE to properly assess the causality of the event to the study device or to a study procedure.

This review would include the subjects' description of the event, study device uploads and medical records (if applicable) from the treating facility. These records will be made available to sponsor. Investigators should classify the relationship between the AE and the study device or study procedures using one of the four possible causality categories listed below:

- **Not related:** relationship to the device, comparator, or procedures can be excluded when:

- the event has no temporal relationship with the use of the investigational device or the procedures related to the application of the investigational device;
- the event does not follow a known response pattern to the medical device (if the response pattern is previously known) and is biologically implausible;
- the discontinuation of medical device application or the reduction of the level of activation/exposure – when clinically feasible – and reintroduction of its use (or increase of the level of activation/exposure), do not impact on the event;
- the event involves a body-site or an organ not expected to be affected by the device or procedure;
- the event can be attributed to another cause (e.g., an underlying or concurrent illness/ clinical condition, an effect of another device, drug, treatment or other risk factors);
- the event does not depend on a false result given by the investigational device used for diagnosis, when applicable;

In order to establish the non-relatedness, not all the criteria listed above might be met at the same time, depending on the type of device/procedures and the event.

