- **Possible:** the relationship with the use of the investigational device, comparator, or the relationship with procedures, is weak but cannot be ruled out completely. Alternative causes are also possible (e.g., an underlying or concurrent illness/clinical condition or/and an effect of another device, drug or treatment). Cases where relatedness cannot be assessed, or no information has been obtained should also be classified as possible.
- **Probable:** the relationship with the use of the investigational device, comparator, or the relationship with procedures, seems relevant and/or the event cannot reasonably be explained by another cause.
- **Causal relationship:** the event is associated with the investigational device, comparator, or with procedures beyond reasonable doubt when:
 - the event is a known side effect of the product category the device belongs to or of similar devices and procedures;
 - the event has a temporal relationship with investigational device use/application or procedures;
 - the event involves a body-site or organ that
 - the investigational device or procedures are applied to;
 - the investigational device or procedures have an effect on;
 - the event follows a known response pattern to the medical device (if the response pattern is previously known);

- the discontinuation of medical device application (or reduction of the level of activation/exposure) and reintroduction of its use (or increase of the level of activation/exposure), impact on the event (when clinically feasible);
- other possible causes (e.g., an underlying or concurrent illness/clinical condition or/and an effect of another device, drug or treatment) have been adequately ruled out;
- harm to the subject is due to error in use;
- the event depends on a false result given by the investigational device used for diagnosis, when applicable;

In order to establish the relatedness, not all the criteria listed above might be met at the same time, depending on the type of device/procedures and the event.

Example: A severe hyperglycemia AE with the following event description would have the following causality assessment for device relatedness:

Improved glucose without an infusion set/site change	Not related
Changed infusion set with glucose improvement	Possible
Infusion set fell out, bent cannula, occlusion alarm	Causal relationship

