12.1 Clinical Events Committee

A clinical events committee (CEC) consisting of external physicians with an expertise in endocrinology and the management of diabetes including insulin pumps and CGM will be convened. The CEC will review AEs as required per protocol, which include reports of:

- Serious adverse event
- Serious adverse device effect
- Unanticipated adverse device effect
- Severe hypoglycemia
- Diabetic ketoacidosis
- Diabetic hyperglycemic hyperosmolar syndrome
- Severe hyperglycemia

CEC is to review and adjudicate unanticipated adverse device effects (UADE), device related DKA, device related HHS, and device related severe hypoglycemia within 10 business days from the time that the sponsor is notified. Adjudication will occur once all applicable documentation has been

received and reviewed by the CEC.

The CEC will assess events to determine agreement or disagreement with the investigator classification of an event.

If the CEC disagrees with the investigator's classification of the event, the rationale will be provided to the investigator. If the investigator agrees with the CEC's adjudication, the CRF documenting the AE will be updated accordingly.

If the investigator does not agree with the CEC's adjudication classification, both determinations will be provided within the final report; however, the CEC's adjudication will be used for data analysis. The disagreement will also be included in reporting to IRBs and regulatory authorities, if required.

The CEC may review applicable information for device related AEs which may include:

- Whether or not the event was unanticipated
- Review of sensor data from CareLink Personal/CareLink system software report (when applicable)
- Review of pump data from CareLink Personal/CareLink system software report (when applicable)
- Misuse of the device by the user

Review of events may require the following information. Final disposition may be delayed based on obtaining this information:

- Monitoring by sponsor at investigational center
- Device return and failure analysis
- CareLink Personal/CareLink system software upload and review of software reports
- Subject clarification to investigational center regarding details about the event
- Source documents that support event: Paramedic records; ER records; Lab records; Hospital admission and discharge summary

The following factors should be carefully considered in the CEC's recommendation to sponsor:

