1. Was the severe hypoglycemia, HHS or DKA related to the AHCL algorithm, or was it related to a known insulin pump risk? For example, a question that may be considered in HHS or DKA would be whether the event was related to an infusion set issue or caused by the AHCL algorithm.
2. Another important consideration would be if the severe hypoglycemia, severe hyperglycemia, HHS or DKA event was related to a device malfunction versus patient non-compliance. For example, if a software anomaly leading to an under-delivery of insulin is discovered versus the subject repeatedly ignoring alarms prompting the subject to take action.

3. Severe hypoglycemia, severe hyperglycemia, HHS or DKA caused directly by an infusion set issue when the study pump is functioning as intended would likely result in acceptance to proceed with the study versus severe hypoglycemia, HHS or DKA that are directly caused by the AHCL algorithm or a device malfunction might stop study enrollment or entire study altogether.
4. It should be noted that the final determination of causality related to 780G system that is made by the CEC may include additional factors which the members consider to be clinically relevant and important.

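### The 10-business-day CEC deadline depends on a first call of device related, so a death, DKA, HHS or severe hypoglycemia first called not related is reviewed without a due date

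*Protocol*

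**What the plan says.** Three places in the protocol use the same event list.

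- **9.9 Study Stopping Rules.** The DMC may stop the study if it finds serious safety problems. The grounds it may rely on include this one: "the occurrence of certain types of individual adverse events (i.e. UADE, device related DKA, device related HHS and device related Severe Hypoglycemia". Such events must first have had expedited CEC adjudication.
- **12.1 Clinical Events Committee.** A limit of 10 business days, counted from when the sponsor is told, is set for this list: "CEC is to review and adjudicate unanticipated adverse device effects (UADE), device related DKA, device related HHS, and device related severe hypoglycemia".
- **12.2 Data Monitoring Committee, third function.** For the same four types, the DMC meets within 10 business days of CEC adjudication.

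The CEC's overall remit in 12.1 is wider. It reviews all SAEs (which include deaths), SADEs, UADEs, severe hypoglycemia, DKA, HHS and severe hyperglycemia, whatever the causality, but that list carries no time limit. Its task is stated as: "The CEC will assess events to determine agreement or disagreement with the investigator classification of an event". Where the CEC and the investigator still disagree, the CEC's "adjudication will be used for data analysis".

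The DMC otherwise meets about every 90 days, sees the rates of all SAEs, severe hypoglycemia, DKA and HHS, and can meet ad hoc.

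**The concern.** The deadline is tied to the judgment that the CEC is there to check. A wrong first call of not related is the error that adjudication should catch, and the same call takes the event off the clock. The DMC's 10 days run from adjudication, so an open-ended CEC step leaves the DMC step open-ended too.

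This matters because the study is single arm, is classed by the sponsor as significant risk (10.5), and has every subject in the study period using the algorithm. The CEC is also asked a specific question that a site may not be well placed to settle at once: "Was the severe hypoglycemia, HHS or DKA related to the AHCL algorithm, or was it related to a known insulin pump risk". What is at stake is how soon an independent look happens, not whether it happens.

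**Working it through.** **1. Whose call is it?** The protocol does not say who decides that an event is device related for the purpose of the deadline. The clock starts at sponsor notification, before the CEC has adjudicated. The label must therefore be a first call by the site or the sponsor.

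**2. Which path does each event take?**

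| Event as first classified | CEC review | CEC deadline | Event-triggered DMC meeting |
|---|---|---|---|
| UADE | yes | 10 business days | 10 business days after adjudication |
| DKA, HHS or severe hypoglycemia, device related | yes | 10 business days | 10 business days after adjudication |
| DKA, HHS or severe hypoglycemia, not related | yes | none stated | none unless the CEC reclassifies, and then dated only from that adjudication |
| Death, not related | yes, as an SAE | none stated | none stated, unless the CEC reclassifies it into a listed type |

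**3. Length of the timed path.** 10 + 10 = 20 business days, or 4 weeks, about 28 calendar days from notification. This is nominal: "Adjudication will occur once all applicable documentation has been" received and reviewed. On the untimed path, the only dated backstop is the routine DMC meeting about every 90 days, roughly the length of one subject's study period.

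**4. Deaths.** Under 11.6, a device that "could have possibly caused the event and therefore is related to the study device or procedure" counts as related, so a possible cause is enough. A device-related death is timed if it is a UADE or the outcome of a device-related DKA, HHS or severe hypoglycemia. One further case may fall outside. Table 4 (10.1) lists cardiovascular event and death among the risks of hypoglycemia under closed loop, and 11.7 treats anything identified in the protocol as anticipated. A device-related cardiovascular death with hypoglycemia that did not meet the severe hypoglycemia definition could then be neither a UADE nor a listed type.

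**5. Workload of removing the causality condition.** The number entering the Phase 2 study period is at least 300 (8.1), for about 90 days each (section 5).

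Patient-years = 300 × 90 / 365.25 = 73.9.

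The documents give no event rates, so the rates below are assumptions. They are combined rates of the newly covered events. The mean count is rate × 73.9 / 100, and the chance of at least one is 1 − exp(−mean).

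| Assumed rate per 100 patient-years | Extra CEC reviews | Chance of at least one |
|---|---|---|
| 0.5 | 0.37 | 31% |
| 1 | 0.74 | 52% |
| 2 | 1.48 | 77% |
| 5 | 3.70 | 98% |

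Counting run-in as well, 300 × 135 / 365.25 = 110.9 patient-years, which gives 0.55 to 5.54 reviews over the same rates. That overstates run-in time for these 300, because subjects who transitioned from Phase 1 skipped Visits 2 to 8 (SAP section 5).

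These figures size the cost of the change. They do not estimate how many events would be wrongly called.

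**The case against.** The case for leaving the text alone is strong on several points, and these stand.

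- **Unclear events already go on the timed path.** Section 11.6 reserves *not related* for cases where the relationship can be excluded, and sends anything that cannot be assessed to *possible*. Only a confident but wrong call is left.
- **The DMC step is partly covered.** If the CEC reclassifies an event as device related DKA, HHS or severe hypoglycemia, the present wording of 12.2 can start the DMC's 10 days. The missing date is the CEC's.
- **Other oversight exists.** The list in 9.9 is introduced as an inclusion, so the DMC may act on other safety issues. It sees rates of all SAEs whatever the causality and can meet ad hoc, and the sponsor can suspend the study (16.10).
- **Subjects have some direct protection.** Table 3 has them switch to injections on hospital admission for any reason until the issue resolves. Section 9.8 requires withdrawal after one severe hypoglycemia, DKA or HHS related to SmartGuard. The withdrawal rule rests on the same causality judgment, so it helps less where that judgment is wrong.

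Three stronger readings are tempting but unsupported. First, a reader might infer that events called not related escape independent review. They do not; only the date is missing. Second, a reader might subtract 28 days from 90 and report the difference as the delay. That sets a worst case against a nominal best case. If events fall evenly between routine meetings, the mean wait is about 90 / 2 = 45 days, and about 28 / 90 = 31% of events reach a routine meeting within 28 days. Third, the worked example in 11.6, which grades "Improved glucose without an infusion set/site change" as not related, might be taken as evidence that sites will miscall the events at issue. It concerns severe hyperglycemia, which has no expedited path, and it says nothing about how DKA, HHS, severe hypoglycemia or death would be graded.

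**Conclusion.** The point holds as a low-cost improvement. No text sets a CEC deadline for a death, DKA, HHS or severe hypoglycemia first called not related, although the CEC must review each of these and check that call. Two residual groups remain: events confidently but wrongly called not related, and possibly an anticipated device-related death outside the four listed types.

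The documents do not allow the number of wrongly called events to be estimated, and none is claimed here. Nor do they show a breach or a failure of oversight. The conclusion rests on reading device related in 12.1 as a call made before adjudication, which follows from when the clock starts, and on finding no other CEC time limit in the protocol or SAP.

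**What to change.** For Phase 2:

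1. In 12.1, apply the 10-business-day CEC adjudication to every death and every DKA, HHS and severe hypoglycemia in a subject using the study pump, whatever the initial causality.
2. In 9.9 and in the third function of 12.2, state that the DMC's 10-business-day meeting also applies to any such event, including a death, that the CEC finds device related or for which it cannot exclude device relation.

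No new data collection is needed: 11.4 already asks sites to report all these events as soon as possible, ideally within 24 hours, whatever the causality. The cost is protocol wording plus the few faster reviews sized above, by a committee already convened. Some of those reviews will be of events that prove unrelated. An extra DMC meeting follows only where the CEC finds, or cannot exclude, device relation.

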10.1 Potential Risks

The potential residual risks and mitigations associated with the devices used during this study are listed in **Table 4**. Risks associated with the commercially available devices used in the study are listed in the associated device labeling/user guides/instructions for use or report of prior investigations.

The clinical investigation has been designed to involve as little pain, discomfort, fear and any other foreseeable risk as possible for the subjects, and both the risk threshold and the degree of distress are specifically defined in the CIP and constantly monitored.

Table 4. Risks, Prevention and Mitigation

Risks with Infusion Sets	Prevention and Mitigation

Risks with infusion sets may include:
 
 • Localized infection • Skin irritation/redness • Bruising • Discomfort/pain • Bleeding • Irritation • Rash • Hyperglycemia secondary to infusion set occlusion or infusion site failure including DKA or HHS • Hyperglycemia secondary to site falling off including DKA or HHS • Anxiety associated with insertion 	
Prevention and mitigation include:
 
 • Follow the provided user guides for insertions and care of infusion sets. • If an infusion site becomes irritated or inflamed, the infusion set will be removed and another set placed in a new location. • In case of hyperglycemia secondary to infusion set occlusion, remove current infusion set and replace with new infusion set and give correction insulin if needed with syringe. • Follow the provided user guides for insulin pump management. • Train prior to study device use on appropriate device use and diabetes management principles and instruct to call investigator with problems.
Risks with Insulin Administration and Pumps	Prevention and Mitigation

Risks with the use of an insulin infusion pump may include the risk of malfunction of the components of the system (pump, software, infusion set and reservoir) as well as the risk of use error during use of the system. DDs or use errors can result in administration of too much or too little insulin which can lead to the following clinical consequences:
 
 • Hypoglycemia • Hyperglycemia • Diabetic ketoacidosis or HHS • Severe hypoglycemia with or without associated seizure, coma or death • Kinked cannula leading to hyperglycemia • Infusion set disconnection from pump leading to hyperglycemia • Subject removes the reservoir from the pump but forgets to disconnect the infusion set from the body which results in hypoglycemia or severe hypoglycemia • Dislodged cannula leading to hyperglycemia • A pump error may lead to under delivery or over-delivery of insulin • Battery failure – no insulin delivered • Insulin deterioration leading to hyperglycemia • Incomplete priming; fails to prime tubing and/or cannula, leading to hyperglycemia 	
Prevention and mitigation include:
 
 • Follow the provided user guides & instructions for insulin and insulin pump management which includes information on infusion set change. • Train prior to study device use on appropriate device use and diabetes management principles and instruct to call investigator with problems. • Instruct to check their meter glucose if their high or low symptoms do not match their sensor alerts or SG readings in order to make diabetes treatment decisions. • Instruct to check their meter glucose if there are any concerns that the SG value is not accurate. • Instruct to have glucose and glucagon on hand for hypoglycemia. • Instruct to change infusion set if suspected catheter occlusion or administer insulin with syringe for persistent hyperglycemia especially if ketones develop.


 Remove a reservoir, without suspending and reconnecting after a while resulting in a hypoglycemia Patient not filling pump reservoir when needed leading to hyperglycemia Magnetic resonance imaging resulting in pump transmitter malfunction Inaccurate insulin delivery due to sudden altitude changes. Hypoglycemia or hyperglycemia from manual bolus Hypoglycemia or hyperglycemia from the use of the SmartGuard feature where SG values may be used to calculate insulin bolus amounts Hypoglycemia or hyperglycemia from computer hacking 	

Risks with hyperglycemia may include:
 
 Diabetic ketoacidosis or HHS Symptomatic ketosis Cardiovascular event Dehydration Potassium and sodium imbalance Shock Altered mental status Coma Acidosis 	
Prevention and mitigation include:
 
 Follow the provided user guides for insulin pump management. Train prior to study device use on appropriate device use and diabetes management principles and instruct to call investigator with problems. Instruct to check their meter glucose if their high symptoms do not match their sensor alerts or SG readings in order to make diabetes treatment decisions. Instruct to check their meter glucose if there are any concerns that the SG value is not accurate. Alternative method of managing glucose levels will be available (insulin and syringe for example).

Risks with hypoglycemia may include:
 
 Seizure Coma Altered mental status Loss of consciousness Cardiovascular event Death Risk of rebound hyperglycemia with ketosis 	
Prevention and mitigation include:
 
 Follow the provided user guides for insulin pump management. Train prior to study device use on appropriate device use and diabetes management principles and instruct to call investigator with problems. Instruct to check their meter glucose if their low symptoms do not match their sensor alerts or SG readings in order to make diabetes treatment decisions. Instruct to check their meter glucose if there are any concerns that the SG value is not accurate). Instruct to have glucose and glucagon on hand for hypoglycemia.
Risk with Sensors	Prevention and Mitigation


Risks with sensors may include:
 
 • Skin irritation or reaction to adhesives • Bruising • Discomfort • Redness • Bleeding • Pain • Rash • Infection • Irritation from tapes used with glucose-sensing products • Raised bump • Appearance of a small "freckle-like" dot where needle was inserted • Allergic reaction • Syncopal episode secondary to needle insertion • Soreness or tenderness • Swelling at insertion site • Sensor fracture, breakage or damage • Minimal blood splatter associated with sensor needle removal • Residual redness associated with adhesive and/ or tapes • Scarring • Scab • Blister • Itchiness • Inflammation • Anxiety • Incorrect SG reading results in incorrect diabetes management • Subject over-treating secondary to alarms which can result in hyperglycemia or hypoglycemia 	
Prevention and mitigation include:
 
 • Follow the provided user guides for insertions and care of sensors. • If a sensor site becomes infected or inflamed, the sensor will be removed and another sensor placed in a new location. • Instruct to check their meter glucose if their high or low symptoms do not match their sensor alerts or SG readings in order to make diabetes treatment decisions. • Instruct to check their meter glucose if there are any concerns that the SG value is not accurate. • Instruct if there are no sensor values, no treatment decisions will be made until a BG is confirmed.
Risks with Transmitter	Prevention and Mitigation

Risks with transmitter may include:
 
 • Skin irritation or reaction to adhesives • Bruising • Discomfort • Redness • Pain • Rash • Infection • Irritation from tapes used with glucose-sensing products • Raised bump 	
Prevention and mitigation include:
 
 • Follow the provided user guides. • Train on the proper use of the transmitters.

 • Allergic reaction • Soreness or tenderness • Residual redness associated with adhesive and/ or tapes • Scarring • Scab • Blister • Itchiness • Inflammation 	
Risks with Serter	Prevention and Mitigation

Risks with serters may include:
 
 • Improper insertion may lead to device performance issue 	
Prevention and mitigation include:
 
 • Follow the provided user guides for insertions and care of device. • Train on the proper use of the serter and skin preparation prior to insertion.
Risks with Fingersticks and Blood Draws	Prevention and Mitigation

Risks with frequent fingerstick testing and blood draws may include:
 
 • Potential risks associated with frequent meter testing of BG and blood ketones include discomfort and ecchymosis at tips of fingers • Potential risks associated with fingerstick testing include discomfort and bruising • Potential risks associated with drawing blood include discomfort, bruising and hematoma 	
Prevention and mitigation include:
 
 • Follow the provided user guides for use of the study meter with fingerstick testing. • Train on the proper use of the study meter and fingerstick testing. • Blood draws will be performed by a trained healthcare professional
Risk with Closed Loop Therapy	Prevention and Mitigation

Risks with Closed Loop may include:
	
Prevention and mitigation include:
 
 • Follow the provided user guides for insulin pump management. • Train prior to study device use on appropriate device use and diabetes management principles and instruct to call investigator with problems. • Instruct to check their meter glucose if their high or low symptoms do not match their sensor alerts or SG readings in order to make diabetes treatment decisions. • Instruct to check their meter glucose if there are any concerns that the SG value is not accurate. • Instruct if there are no sensor values, no treatments decision will be made until a BG is confirmed. • Instruct to have glucose and glucagon on hand for hypoglycemia.


 • Hypoglycemia • Severe hypoglycemia • Hyperglycemia • Diabetic ketoacidosis or HHS • User entry error 
 ○ Patient administering boluses by entering false carb doses leading to hypoglycemia or hyperglycemia ○ Patient entering false glucose values for any reason leading to hypoglycemia and hyperglycemia ○ Patient entering false BG values for calibration leading to hypoglycemia or hyperglycemia • Sensor failure resulting from patient failure to calibrate leading to hypoglycemia or hyperglycemia • Sensor over-reading resulting in hypoglycemia • Sensor under-reading resulting in hyperglycemia • Sensor missed transmission, or any other fault resulting in no SG value, leading to hyperglycemia or hypoglycemia • Voluntary insulin delivery (with the pump or with a syringe) immediately prior to entering SmartGuard may result in severe hypoglycemia despite shutting down insulin delivery by the algorithm • Hypoglycemia related to patient taking insulin via injection while in Closed Loop (SmartGuard) • Hypoglycemia or hyperglycemia related to entering or exiting Closed Loop (SmartGuard) • Insulin over-delivery due to potential interference from acetaminophen • Cyber security hacking into pump 	
 • Instruct to avoid the use of products containing acetaminophen. • If acetaminophen is taken, subjects will be instructed to use additional BG meter readings to verify their glucose levels. • If acetaminophen is taken, while the SmartGuard feature is active, subjects will be instructed to use the temp target feature (when used, Auto Correction is not available). • Instruct subjects that in case of prolonged use of acetaminophen, the temp target feature can be used repeatedly and in succession. • Pump has cybersecurity encryptions to prevent hacking.

Risks with hyperglycemia may include
 
 • Diabetic ketoacidosis or HHS • Symptomatic ketosis • Cardiovascular event • Dehydration • Potassium and sodium imbalance • Shock • Altered mental status • Coma • Acidosis 	
Prevention and mitigation include:
 
 • Follow the provided user guides for insulin pump management. • Train prior to study device use on appropriate device use and diabetes management principles and instruct to call investigator with problems. • Instruct to check their meter glucose if their high symptoms do not match their sensor alerts or SG readings in order to make diabetes treatment decisions.

	
 • Instruct to check their meter glucose if there are any concerns that the SG value is not accurate. • Instruct if there are no sensor values, no treatments decision will be made until a BG is confirmed.

Risks with hypoglycemia may include:
 
 • Seizure • Coma • Altered mental status • Loss of consciousness • Cardiovascular event • Death • Risk of rebound hyperglycemia with ketosis 	
Prevention and mitigation include:
 
 • Follow the provided user guides for insulin pump management. • Train prior to study device use on appropriate device use and diabetes management principles and instruct to call investigator with problems. • Instruct to check their meter glucose if their low symptoms do not match their sensor alerts or SG readings in order to make diabetes treatment decisions. • Instruct to check their meter glucose if there are any concerns that the SG value is not accurate. • Instruct if there are no sensor values, no treatment decisions will be made until a BG is confirmed. • Instruct to have glucose and glucagon on hand for hypoglycemia.
Risk with Acetaminophen Use	Prevention and Mitigation

Potential risks with acetaminophen may include:
 
 • False elevation of SG readings potentially resulting in an over-delivery of insulin which may cause hypoglycemia. The level of inaccuracy depends on the amount of acetaminophen active in subject's body and may be different for each subject • Liver damage, liver failure and/or rare but fatal liver failure can occur • Skin rash and/or serious and potentially fatal skin reactions have been reported • Allergic reactions including those which are serious and potentially fatal can occur • Kidney disease • Lowered blood counts (red cells, and white cells) 	
Prevention and mitigation include:
 
 • Follow the user guide. • Instruct to avoid the use of products containing acetaminophen. • If acetaminophen is taken, subjects will be instructed to use additional BG meter readings to verify their glucose levels. • If acetaminophen is taken, while the SmartGuard™ feature is active, subjects will be instructed to use the temp target feature (when used, Auto Correction is not available). • Instruct subjects that in case of prolonged use of acetaminophen, the temp target feature can be used repeatedly and in succession.

